3.3. Strata and Covariates

Not applicable.

3.4. Examination of Participant Subgroups

Selected efficacy endpoints (e.g., ORR, DOR, PFS, and OS) in the cohorts below will be summarized by different subgroups as specified below:

- Endometrial carcinoma: Prior chemotherapy and immunotherapy vs Without prior immunotherapy
- HNSCC: HPV positive vs HPV negative/missing; Oropharynx carcinoma vs Non-Oropharynx carcinoma
- SCLC: Chemotherapy-free Interval (CTFI) < 90 Days vs Chemotherapy-free Interval (CTFI) \geq 90 Days; Gender; Age group : < 65 years old vs \geq 65 years old; Responders (best response with CR or PR) vs non-responders (best response with SD and PD) vs Non-responders (best response with SD, PD and not reported/not available) in last anti-cancer therapy.

For the SCLC cohort, the chemotherapy-free interval (CTFI) is defined as the time from the last dose of chemotherapy (includes Carboplatin and Cisplatin) to the occurrence of disease progression in the prior anti-cancer therapy.

Additionally, for all cohort, the TEAE summary table will be examined by age group (< 65 years vs \geq 65 years).

3.5. Multiple Comparisons

Not applicable.

3.6. Data Handling Conventions and Transformations

Baseline value is defined as the last measurement that was observed on or prior to the date of first dose, unless otherwise specified.

See [Appendix 2](#) for details.

3.7. Assessment of COVID-19 Impact

This study was ongoing during the novel coronavirus (COVID-19) pandemic, which has an impact on the study conduct. Some participants were unable to attend onsite visits due to the “shelter-in-place” guidelines, site closures, and/or other reasons. Since this study’s database does not specifically collect any COVID-19 related information, no analysis will be conducted to assess COVID-19 impact.

4. PROTOCOL DEVIATIONS

Participants who did not meet at least one eligibility criterion for study entry but enrolled in the study will be summarized by cohort based on the All Enrolled Analysis Set. The summary will also present the number and percent of participants who did not meet specific criteria.

Protocol deviations occurring after participants entered the study are documented during routine monitoring. The number and percent of participants with important protocol deviations and the total number of important protocol deviations by deviation reason (e.g., nonadherence to study drug, violation of select inclusion/exclusion criteria) will be summarized by cohort for the Full Analysis Set.

5. PARTICIPANT INFORMATION

5.1. Participant Enrollment and Disposition

Key study dates (i.e., first participant enrolled, last participant enrolled, last participant last visit for the primary endpoint) will be provided.

A summary of participant enrollment will be provided by cohort for each country.

A summary of participant disposition will be provided by cohort based on the Enrolled Analysis Set. This summary will present the number of participants enrolled, and the number of participants in each of the categories listed below:

- The treated participants (received at least 1 dose of study drug)
- Continuing treatment
- Discontinued from treatment with reasons for discontinuation of treatment
- Continuing on study
- Discontinued from study with reasons for discontinuation of study

A by-participant listing for disposition will be provided for the Enrolled Analysis Set, including their informed consent dates, first/last dose dates, discontinued from treatment date/reason and discontinued from study date/reason.

5.2. Extent of Study Drug Exposure

Treatment exposure will be summarized for the Safety Analysis Set using the following measures:

- Number of doses administered
- Descriptive statistics of duration of treatment (months), along with number of participants with treatment duration longer than or equal to 3 months, 6 months, 12 months, and 24 months; Duration of treatment (in days) will be calculated as (date of the last non-zero dose – date of the first non-zero dose + 1) and converted to months by dividing by 30.4375
- Number and percent of participants with dose reduction according to percent of dose reduction (25% or 50% dose reduction per CRF form as the dose level of sacituzumab govitecan is only allowed to reduce from 10 mg/kg to 7.5 or 5 mg/kg) and reasons for dose reduction
- Descriptive statistics of time to first dose reduction.

- Relative dose intensity (RDI) will be calculated as described below in section 5.2.2 and summarized. Cumulative dosage and relative dose intensity will be summarized by descriptive statistics, and relative dose intensity will be additionally summarized by the categories (e.g., < 70%, 70% to < 90%, 90% to < 110%, \geq 110%).

5.2.1. Administered Dosage

Administered dose (mg) for each infusion is calculated per CRF form from (“Dose calculated” \times “Actual volume administered”/“Total volume prepared”).

Administered dosage (mg/kg) of each infusion in a cycle is calculated by dividing the administered dose (mg) by most recent weight (kg) prior to current dosing.

5.2.2. Relative Dose Intensity

Total amount of study drug administered (mg/kg) for each participant is defined as the sum of all administered dosages (mg/kg) of all infusions the participant received in the study.

Relative dose intensity (RDI) (%) for each participant is calculated: dividing the participant’s total amount of study drug administered dosage (mg/kg) by the total amount of study drug expected to be administered (mg/kg).

$$\text{RDI (\%)} = \frac{\text{Total amount of study drug administered (mg/kg)}}{10 \text{ (mg/kg)} * \text{number of planned SG doses}} \times 100$$

$$\text{Number of Planned Doses} = \left(\frac{\text{Last Nonzero Dose Date} - \text{First Nonzero Dose Date} + X}{21} \right) * 2$$

- If the remainder $\left(\frac{\text{Last Nonzero Dose Date} - \text{First Nonzero Dose Date} + 1}{21} \right) \leq 7$, the number of expected doses in the last cycle is 1, and $X = \frac{21}{2} * 1 - 0 = 10.5$.
- If the remainder $8 \leq \left(\frac{\text{Last Nonzero Dose Date} - \text{First Nonzero Dose Date} + 1}{21} \right) < 21$, the number of expected doses in the last cycle is 2, and $X = \frac{21}{2} * 2 - 7 = 14$.

The RDI calculation will be performed using the general formula above and details are described in programming specifications.

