#### **1.1.3.3. Summary of Sacituzumab Govitecan Safety Data**

The safety profile of sacituzumab govitecan has been characterized based on 795 patients who received a starting dose of 10 mg/kg of sacituzumab govitecan in Studies IMMU-132-01 (N = 402, regardless of tumor type; data cutoff date 01 March 2019), IMMU-132-05 (N = 258; data cutoff date 11 March 2020), and IMMU-132-06 (N = 135; data cutoff date 18 September 2020). As of the data cutoff dates for these studies, the median treatment duration was 4.1 months (6 cycles). The following is a summary of the safety profile; additional details can be found in the current edition of the Investigator's Brochure.

Nearly all subjects experienced at least 1 AE; approximately 77% of subjects experienced at least 1 National Cancer Institute-Common Terminology Criteria for Adverse Events (NCI-CTCAE)  $\geq$  Grade 3 AE; 37% experienced at least 1 serious adverse event (SAE). The protocol provided instructions for dose reduction and dose interruption, and treatment discontinuation based on toxicities. AEs led to treatment interruption in 55% of subjects; however, only 8% of subjects discontinued because of AEs. Fatal AEs (within 30 days of the last dose) occurred in 2% of subjects; 2 were assessed as treatment-related (sepsis in the setting of febrile neutropenia in a subject with UC; aspiration pneumonia in the setting of disease progression in a subject with NSCLC who had persistent nausea and vomiting after each infusion of sacituzumab govitecan).

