## 4. STUDY PROCEDURES

All subjects must be dosed within 28 days of providing written informed consent. Unless otherwise specified, visit windows are within -1 and +2 days for the treatment schedule and  $\pm$  7 days for response assessments. Absolutely no waivers for subject eligibility will be permitted.

Samples for PK, ADA, and biomarker analyses will be collected according to the protocol schedule of assessments and are to be shipped to the Sponsor's designee. Otherwise, all other laboratory procedures are to be performed locally at each study site ([Table 2](#)).

The schedule of assessments for all subjects before implementation of PA5 is presented in [Table 2](#). The schedule of assessments for all subjects who continue treatment following implementation of PA5 is presented in [Table 3](#).

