#### **4.6. Treatment Discontinuation**

Subjects may discontinue the study drug under any of the following conditions:

- 1) Withdrawal of consent from further treatment with study drug.
- 2) Lost to follow-up (see Section [4.6.1](#)).
- 3) An AE that, in the opinion of the Investigator or the Sponsor, contraindicates further dosing.
- 4) Initiation of alternative anti-tumor therapy, including any other investigational product.
- 5) Pregnancy.
- 6) More than a 3-week dose delay from the planned treatment date due to treatment-related toxicity or 5-week dose delay for all other reasons.
- 7) PD without evidence of clinical benefit with continued therapy.
- 8) Subject non-compliance.
- 9) Suspension of the study by the Sponsor.
- 10) Death.
- 11) Investigator's or treating physician decision in the absence of any of the above.

Study drug discontinuation should not result in subject discontinuation from the study, and the subject should continue to be followed up in the study for disease progression and survival per Section [4.7](#). Reasons for discontinuation from the study are described in Section [4.8](#).

If a subject discontinues study treatment (eg, as a result of an AE), every attempt should be made to keep the subject in the study and continue to perform the required study-related follow-up procedures (see Section [4.7](#)). If this is not possible or acceptable to the subject or Investigator, the subject may be withdrawn from the study.

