## **5. STUDY EVALUATIONS**

All subjects must be dosed within 28 days of providing written informed consent. No subject may be dosed until the Sponsor or their representative has approved the eligibility packet. Clear documentation as to the reason the subject was not dosed should be provided on the relevant eCRF. Unless otherwise specified, visit windows are permitted either 1 day before or + 2 days after scheduled visits and  $\pm$  7 days for response assessments. Treatment delays for reasons other than required for resolution of treatment-related toxicity are not permitted.

CCI

CCI

CCI

CCI

CCI

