**Table 3. Modified Schedule of Assessments/Study Calendar (After Implementation of PA5)**

Visit	Treatment		EOT Visit b	30-Day Safety Follow-up Visit c
Cycle	ALL Cycles			
Day a	1	8		
Weight d	X		X	X
Physical examination e	Per standard of care		X	X
Vital signs f	As needed			
Study drug administration	X	X		
Urine Pregnancy test (if applicable) g	X		X	X
Serum Follicle-Stimulating Hormone (FSH) h	As needed			
Hematology i	X	X	X	X
Serum chemistry including liver function tests j	X	X	X	X
Tumor assessment (CT or MRI scan) k	Per standard of care			
AE reporting l	X	X	X	X
Prior/concomitant medications	X	X	X	X
Subsequent anti-cancer treatment				X

Abbreviations: AE = adverse event; ALT = alanine aminotransferase; ANC = absolute neutrophil count; AST = aspartate aminotransferase; BUN = blood urea nitrogen ; CBC = complete blood count; CT = computed tomography; eCRF = electronic case report form; EOT = end of treatment; MRI = magnetic resonance imaging; PA5 = Protocol Amendment 5; SAE = serious adverse event.

- a Unless otherwise specified, visit windows are within -1 to +2 days of the schedule visits and  $\pm 7$  days for response assessments.
- b The EOT Visit should occur within 30 days of the decision to discontinue treatment. If the EOT Visit and 30-Day Safety Follow-up Visit occur within 14 days of each other, the same assessment results may be utilized for both study visits.
- c The Safety Follow-up Visit should be conducted 30 days ( $\pm 3$  days) after the last dose of study drug.
- d During treatment, subject's body weight will be measured on Day 1 of each treatment cycle (or more frequently if the subject's body weight changed by >10% since the previous administration), at the EOT Visit, and at the 30-Day Safety Follow-up Visit.
- e Complete physical examinations will be performed at the EOT Visit and the 30-Day Safety Follow-up Visit. At study visits during the Treatment Phase, physical examinations should be performed per institutional practice.
- f Collection of vital signs will be needed in the event of suspected infusion-related reaction. Vital signs will include blood pressure, heart rate, pulse, respiratory rate, and body temperature and will be taken after the subject has been resting for at least 5 minutes.

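### SAP 5.2.2 treats a last Day-8 dose given one day early, within the visit window, as a one-dose cycle, so full in-window dosing can be reported as RDI of 110% or more.

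*SAP*

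**What the plan says.** SAP 5.2.2 defines RDI as the total mg/kg given, divided by 10 mg/kg times the number of planned doses. Planned doses are (last − first non-zero dose date + X)/21 × 2. X depends on the remainder of (last − first + 1)/21. At 7 or less, "the number of expected doses in the last cycle is 1" and X = 10.5. From 8 up to 21, two doses are expected and X = 14. The section closes: "The RDI calculation will be performed using the general formula above and details are described in programming specifications".

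SAP 5.2 reports RDI with descriptive statistics and in bands: "relative dose intensity will be additionally summarized by the categories (e.g., < 70%, 70% to < 90"%, then 90% to below 110%, and 110% or more.

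The protocol gives the same dosing window in three places:
- Section 4: "visit windows are within -1 and +2 days for the treatment schedule"
- Section 5: "visit windows are permitted either 1 day before or + 2 days after scheduled visits"
- Table 3, footnote a: "visit windows are within -1 to +2 days of the schedule visits"

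**The concern.** The remainder for an on-schedule Day-8 dose is exactly 8, the lowest value that counts as a two-dose cycle. The rule therefore has no tolerance on the early side, although the protocol permits one day early. A participant who received both doses of the last cycle, in window, is assigned the denominator of someone from whom only one dose was expected.

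What is at stake is the exposure table. A reader takes an RDI of 110% or more to mean that clearly more drug was given than planned. Here it would describe participants who were dosed as the protocol allows. No efficacy result depends on RDI.

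**Working it through.** **Inputs.** Dosing is 10 mg/kg on Days 1 and 8 of a 21-day cycle (SAP 1.2). The window is −1 to +2 days (Protocol 4, 5 and Table 3). X and the remainder rule come from SAP 5.2.2. Let d = last − first dose date and r = the remainder of (d + 1)/21. Every dose is taken as exactly 10 mg/kg with none missed, so RDI = doses given / planned doses, with planned = 2(d + X)/21.

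**The plan's own constants.** 21/2 × 1 − 0 = 10.5 and 21/2 × 2 − 7 = 14, as stated. On-schedule dosing returns 100% for a last dose on Day 1 or Day 8 in each of cycles 1 to 8. For example, in cycle 1 with last dose on Day 8, d = 7, r = 8, planned = 2 × 21/21 = 2.

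**Last Day-8 dose one day early, window counted from Cycle 1 Day 1.** In cycle k, d = 21(k − 1) + 6 and r = 7, so X = 10.5.

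| Last cycle | d | Doses | Planned, X = 10.5 | RDI as written | Planned, X = 14 | RDI, X = 14 |
|---|---|---|---|---|---|---|
| 1 | 6 | 2 | 2 × 16.5/21 = 1.571 | 127.3% | 1.905 | 105.0% |
| 2 | 27 | 4 | 2 × 37.5/21 = 3.571 | 112.0% | 3.905 | 102.4% |
| 3 | 48 | 6 | 2 × 58.5/21 = 5.571 | 107.7% | 5.905 | 101.6% |
| 6 | 111 | 12 | 2 × 121.5/21 = 11.571 | 103.7% | 11.905 | 100.8% |

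**Separating the real effect from the artefact.** The X = 14 values exceed 100% because the dose really was early: one day is worth 2/21 = 0.095 of a planned dose. The rule removes 0.429 (2 − 1.571). The extra 0.333 comes from the switch in X (2 × 3.5/21). For comparison, in cycle 1 a Day-8 dose one day late gives 95.5% and two days late 91.3%.

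**Mean dose needed to stay at 110% or more.** Cycle 1: 110/127.3 = 86.4% of 10 mg/kg. Cycle 2: 110/112.0 = 98.2%.

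**If windows run from the current cycle's Day 1.** The visible text does not say which origin applies, and under this reading smaller remainders are also in window:
- Doses on Days 1, 8, 21, 27: d = 26, r = 6, 4/3.476 = 115.1% (X = 14: 4/3.810 = 105.0%).
- Doses on Days 1, 8, 21, 28, 41, 47: d = 46, r = 5, 6/5.381 = 111.5% (X = 14: 6/5.714 = 105.0%).

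**The case against.** The constants are right and on-schedule dosing gives exactly 100%. The rule counts doses due by calendar date, and on study day 7 the Day-8 dose is not yet due, so one expected dose follows that logic. The same logic governs late doses: a last Day-1 dose seven days late has remainder 8 and counts as a two-dose cycle, and nobody calls that wrong. This is coherent, but it does not rescue the early case. Lateness is meant to lower RDI. A permitted one-day shift should not raise it by 27 points when the day itself accounts for 5.

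The practical effect is small, and that stands. A change of category needs a last dose exactly one day early (windows from Cycle 1 Day 1), treatment ending in cycle 1 or 2, and near-full dosing. Median treatment in the earlier studies was 6 cycles (Protocol 1.1.3.3), where the difference is 103.7% against 100.8%. The cycle-2 case is also fragile, because SAP 5.2.1 divides by the most recent weight while the dose is normally set on enrolment weight. Staying at 110% needs 1.10 × 3.571 = 3.929 full-dose equivalents. That leaves 1.929 for cycle 2, so a weight gain above about 3.7% (2/1.929 = 1.037) at both cycle-2 doses brings RDI below 110%.

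The programming specifications might already deal with early doses. Protocol Table 2 and most of Section 7.5.2.5 are redacted, and the windows apply only where nothing else is specified. That limits what can be said about the final output. It does not change the SAP text, and the visible footnotes of Table 3 set no minimum interval between doses.

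**Conclusion.** The concern holds, at minor severity. As written, SAP 5.2.2 gives 127.3% (cycle 1) or 112.0% (cycle 2) to a participant who had every dose in full and in window, with the last Day-8 dose one day early. The cut-off itself contributes 22.3 points (127.3 − 105.0) and 9.6 points (112.0 − 102.4); the rest is genuine early dosing. From cycle 3 RDI is still inflated but stays below 110%.

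This rests on full doses, none missed, and windows counted from Cycle 1 Day 1. Under the other origin the effect can reach later cycles, as the 111.5% example in cycle 3 shows. The documents do not say how many participants are affected, the bands are offered only as examples, and the conclusion concerns the SAP text, not the program.

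**What to change.** Keep the cut-off at 7 and add one exception to SAP 5.2.2. Use X = 14 when the remainder is 7 and the last non-zero dose is recorded as the Day-8 dose of cycle k, where k is the whole part of (last − first)/21, plus 1. State whether dosing windows are counted from Cycle 1 Day 1 or from the current cycle's Day 1; if the latter, apply the same exception at remainders 1 to 6. Align the SAP with the programming specifications.

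The cycle check matters because late doses must keep their present RDI. Interruptions are common: in earlier studies, "AEs led to treatment interruption in 55% of subjects". A 20-day delay is also possible on treatment, since the related discontinuation condition in Protocol 4.6 begins at "More than a 3-week dose delay from the planned treatment date due to treatment-related toxicity". Two simpler changes fail on this point:
- **Moving the cut-off for everyone.** A cycle-4 Day-1 dose six days late (7 doses, d = 69) goes from 7/7.571 = 92.5% to 7/7.905 = 88.6%, a change of category.
- **A Day-8 condition without the cycle check.** Four full doses on Days 1, 8, 22, 49 (d = 48, remainder 7) go from 4/5.571 = 71.8% to 4/5.905 = 67.7%, also a change of category. With the check, the dates imply cycle 3 and the record says cycle 2, so X stays at 10.5.

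Over cycles 1 to 19 and shifts of −8 to +119 days, the exception touches no late Day-8 dose at remainders 1 to 7, and on-schedule participants stay at 100%.

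The cost is a short addition to SAP 5.2.2 and the RDI program, using the recorded cycle and day of the last dose, and a small departure from the sponsor-wide RDI convention noted in SAP 12. One gap remains if windows run from the current cycle: early Day-1 doses are not covered. Doses on Days 1, 8, 21, 28, 41 (d = 40, remainder 20) take X = 14 and give 5/5.143 = 97.2%, against 5/4.810 = 104.0% with X = 10.5. If that origin is chosen, this case needs a sentence too.

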5.3. Demographics and Baseline Characteristics

Participant demographics and baseline characteristics will be summarized with descriptive statistics by cohort for the Full Analysis Set.

Baseline demographic data summaries will include age, age by categories [< 65 years, ≥ 65 years], sex, race, ethnicity.

Baseline characteristics will include but are not limited to: Eastern Cooperative Oncology Group (ECOG) performance status score, and tobacco, alcohol use status.

In particular, for HNSCC cohort, the number of percent of participants with the following baseline disease characteristics will be summarized: HPV status (negative, positive), site of disease (oral cavity, oropharynx, larynx, etc.) and HPV positive with site of disease at oropharynx. For SCLC, the status of prophylactic brain irradiation will be summarized.

A by-participant listing for demographics and baseline characteristics will be provided for the Full Analysis Set.

5.4. Prior Anti-cancer Therapy

The number and percent of participants with different regimens, therapy type (e.g., chemotherapy, hormonal therapy, immunotherapy, targeted agents and other), setting status in last therapy (neoadjuvant, adjuvant, advanced/metastatic, unknown, and other), best response in the last therapy, time from disease progression in last therapy to study entry and last therapy to study entry will be summarized. Study entry refers to the date of first dose of study drug and the last therapy refers to the prior anti-cancer therapy with the last end date before study entry.

For individual cohorts, the number and the percent of participants with the following information below will also be summarized:

HNSCC and Endometrial carcinoma cohorts:

- Chemotherapy + Immunotherapy
- Chemotherapy + Immunotherapy + ≤ 3 Lines of Therapies
- Chemotherapy + Immunotherapy + MSI-H Status (Yes) (for Endometrial cohort Only)

SCLC cohort:

- CTFI < 90 days vs CTFI ≥ 90 days
- Immunotherapy-free interval < 90 days vs ≥ 90 days (similar to CTFI)
- Chemotherapy
 - Carboplatin + Etoposide
 - Cisplatin + Etoposide
- Immunotherapy
 - Atezolizumab
 - Durvalumab
 - Nivolumab

A by-participant listing for prior anti-cancer therapy will be provided for the Full Analysis Set.

5.5. Disease History

Time from initial diagnosis to study entry, stage at initial diagnosis, stage at study enrollment, time from initial diagnosis to confirmed metastatic disease, time from confirmed metastatic disease to study entry, and area of disease involvement at study enrollment will be summarized in the table of disease history. Study entry refers to the date of first dose of study drug.

A by-participant listing for disease history will be provided for the Full Analysis Set.

